## 5.16. Feasibility

Taking into account a mean yearly incidence of acute LRTI in children between one and twelve years old presenting in primary care of around 50/1000 (6, 37) and a practice list size of 6000, 40 children per year would expect to present, and if 1 in 2 are approached (approximately 20 per annum), and that 50% of parents agree to the trial (10 per annum), around 100 participating practices could recruit the sample during one winter. Although these assumption are based on our previous trial in LRTI (which included 100 children) and for other trials of antibiotic strategies in children, (9, 38) it sensible to make conservative assumptions. We will therefore perform initial internal piloting in one centre (5-10 practices) during the first winter to refine study procedures and ensure our assumptions are reasonable, and propose to recruit a minimum of 30 practices in 4 centres, and perform the main recruitment in up to 2 winters. With 1 month follow-up and 5 months data cleaning, analysis and report writing the whole study will take 3 and a half years.

Organisational difficulties, fewer than expected eligible patients, discomfort about patients eligibility and intervention efficacy, and patients' treatment preferences have been prominent issues in many trials, and have been recently described. (39) Unearthing the key problems for recruiters is of central importance in the piloting phase and we anticipate that the issues will become apparent, as they have

in our previous studies, in the process of detailed and sensitive discussion/iteration between an experienced trial manager and the 20-30 recruiting clinicians who are likely to participate in piloting.

## 5.17. Role of funders

The funder will have no role in data collection, analysis, data interpretation, report writing or in the decision to submit for publication.

## 5.18. Nested qualitative studies

### AIMS

- (1) Prior to the start of the study itself, a small student study will be undertaken to explore a range of parent (and child/patient) views to aid the design of study procedures, to help optimize the acceptability of procedures once the trial is operational.
- (2) To explore a range of parent (and child/patient) views on study participation, seeking to understand positive and negative experiences from start to finish.

### TIMING

- (1) Will take place in months prior to the study commencement/randomization.
- (2) Will take place once participants have been randomized and participated.

### METHODS

Semi-structured in-depth interviews will be used, but will be flexible to permit parents to speak freely on topics they deem to be relevant to ensure key emerging issues are captured. A subtle realist approach will be employed throughout the project to help represent participants' views.

### SAMPLE

A purposive sampling approach will be designed to elicit views of a range of parents (and children where appropriate) (including a mix of men and women/boys and girls).

1. 15-20 interviews is likely to be sufficient to gather detailed feedback on parent (children/patients) views to help design the trial procedures.
2. Between 15 and 30 interviews should be adequate to represent the views of a range of parents (children/patients) following participation. Additional interviews will be conducted if saturation has not been reached.

### ANALYSIS

We will follow the stages of Braun and Clarke's thematic analysis, assisted by NVivo (QSR international Pty Ltd) computerized analysis software as necessary. Analysis will aim to identify themes to help fulfil aims 1 and 2 whilst remaining flexible and open to emerging findings.

#### QUALITY

Standard methodological strategies will be employed to help safeguard rigour and ensure we produce trustworthy, plausible, and relevant findings. These will include careful purposive sampling, a clear exposition of methods (including field notes, and audio recording of interviews and accurate transcription of interviews, regular discussion between the fieldworker and senior qualitative researcher (including double coding/discussion of codes). Negative case analysis will help to refine analysis/safeguard against premature completion and the researcher will be tutored in the importance of a 'reflexive' sensitivity to the relationship between the researcher and research process.

### 5.19 Discontinuation / withdrawal of participants from trial

Each participant has the right to discontinue their study medication or withdraw from the study at any time. In addition, the investigator may discontinue a participant's study medication or withdraw a participant from the study at any time if the investigator considers it necessary (e.g. the participant experiences an adverse drug reaction, the participant's parent or guardian withdraws consent, or the investigator considers that further participation in the study would not be appropriate due to the personal circumstances of the participant or the participant's parent or guardian).

#### DISCONTINUATION OF STUDY MEDICATION

Clinicians will be advised to discontinue a participant's study medication if he/she experiences an adverse drug reaction related to the study medication. In addition, clinicians will be advised to prescribe an appropriate non beta-lactam antibiotic if antibiotic treatment is indicated. Parents/guardians of participants whose study medication is discontinued will still be required to complete their study diaries and questionnaires and will still receive telephone follow-up calls unless they choose to withdraw consent for these.

#### WITHDRAWAL

Once a participant withdraws or is withdrawn from the study, no actions will be taken to obtain data other than to monitor adverse events (see section 7.3. Procedures for Recording Adverse Events). Consent to proceed with reviewing the medical notes will be specifically confirmed for participants withdrawn from the study.

### 5.20 Definition of end of trial

The end of the trial will be the date of the last medical notes review of the last trial participant.

### 5.21 Thank you to parents

As a token of our thanks for helping with the study and the time doing the diary we will provide a £10:00 High Street shopping voucher.

## 6. INVESTIGATIONAL MEDICINAL PRODUCT (IMP)

### 6.1. IMP Description

The following drugs are defined as investigational medicinal products (IMP) for this trial

IMP	Dosage form	Strength
Amoxicillin	Oral Suspension (Powder for reconstitution)	250mg/5ml
Placebo for Amoxicillin	Oral suspension (Powder for reconstitution)	N/A

Amoxicillin is a pale yellow powder for reconstitution as suspension. The Amoxicillin product used in this trial will be a product with UK marketing authorisation.

The matching placebo product is formulated with excipients commonly used for antibiotic suspensions. The placebo product will be identical in appearance as a pale yellow powder for reconstitution (see section on treatment blinding). The placebo is formulated with excipients commonly used for antibiotic suspensions.

Both Amoxicillin and placebo will be packed in identical bottles. Each pack of IMP will contain either 3 bottles of Amoxicillin or 3 bottles of placebo, and a unique medication number will be printed on each pack of IMP.

Pilatus Pharma Ltd will be responsible for Qualified Person (QP) release of the IMPs for this trial.

### TREATMENT BLINDING

Participants, their parents/guardians, healthcare professionals at recruiting sites and all research study staff will remain blinded to treatment allocation throughout the trial.

Both Amoxicillin and placebo will be packed in identical bottles. Each pack of IMP will contain either 3 bottles of Amoxicillin or 3 bottles of placebo, and a unique medication number will be printed on each pack of IMP.

## DOSING

Weight (kg)	Dose (for oral administration)	Duration
4.5 to <6.5	100mg (2ml) TDS	7 days
6.5 to <9	150mg (3ml) TDS	7 days
9 to <12	200mg (4ml) TDS	7 days
12 to <15	250mg (5ml) TDS	7 days
15 to <18	300mg (6ml) TDS	7 days
18 to <24	400mg (8ml) TDS	7 days
24 to <30	500mg (10ml) TDS	7 days
30 to <36	600mg (12ml) TDS	7 days
36 +	700mg (14ml) TDS	7 days

## LABELLING

The labelling of medication will conform to Annex 13 EudraLex Volume 4, Guidelines to Good Manufacturing Practice and Article 14 of Directive 2001/20/EC.

Each medication pack label will be printed with a unique medication ID number to ensure Amoxicillin and placebo are indistinguishable, and thus maintain allocation concealment (see 4.8 for the randomisation process).

## SUPPLY OF IMP

Each study site will be supplied by the sponsor with IMP.

## ORDERING OF IMP

Study sites are responsible for notifying the trial manager when IMP stock is getting low. The trial manager is also responsible for monitoring IMP level at study sites.

## DISPENSING

A unique medication number will be printed on each pack of IMP which corresponds to one of the 2 treatment arms. Investigator staff will randomise and dispense by selecting the next sequentially numbered IMP pack.

IMPs are to be dispensed only in accordance with the protocol.

## 6.2. Storage of IMP

IMPs must be received by a designated person at the study site, handled and stored safely and properly, and kept in a secured location to which only the investigator and designated assistants have access. Upon receipt, all IMPs should be stored according to the instructions specified on the drug labels. IMPs are to be kept in a dry place below 25°C. In accordance with stability data any IMP which is found to have gone above 25°C but remains below 30°C must continue to be temperature monitored to ensure it does not go above 30°C nor do so for more than 6 months or 40°C and 3 months the product will be safe to use without the need to reduce shelf life. Study sites must follow the study specific IMP handling Standard Operating Procedure (SOP), and complete the associated storage risk assessment and temperature excursion forms if a temperature deviation occurs.

Participants/parents/guardian will be instructed to store the reconstituted suspension at 2°C-8°C in a refrigerator.

### Temperature excursion

Sites will be asked to report all temperature excursions to the trial manager immediately.

### DISPOSAL OF IMP

Disposal will be at site in accordance with the IMP handling SOP.

## 6.3. Compliance with Trial Treatment

Parents or guardians will be asked to record in their study diaries each dose of study medication given to the child. Children whose study diaries indicate that they received 11 or more doses (75) of trial medication from days 1 to 5 inclusive will be considered to be compliant with trial medication. All randomised trial participants will be included in the intention-to treat population.

## 6.4. Accountability of the Trial Treatment

The investigator or designee must maintain an accurate record of the shipment and dispensing of IMPs. Monitoring of drug accountability will be performed by the trial monitor during site visits and at the completion of the trial.

## 6.5. Concomitant Medication

Trial participants will be advised to continue their usual regular medications while taking part in the trial. Healthcare professionals will record data at baseline on antiviral medications prescribed to participants during their current LRTI episode. Trial participants will be advised to continue taking any antiviral medications prescribed before study entry.

Parents/guardians will be advised that they can give their children additional medications for their LRTI episode while they are in the trial. They will be asked to record these additional medications in the study diary from days 1 to 28.

Since our trial will be double-blinded, clinicians will treat trial participants who re-consult in whatever way they feel is clinically appropriate. We will advise clinicians to prescribe an appropriate non betalactam antibiotic if they feel that antibiotic treatment is indicated in a trial participant who re-consults due to clinical deterioration within 28 days of trial entry.

We will also advise clinicians to prescribe any other medications to participants during the study period if they feel this to be clinically appropriate. A member of the research team will extract data from participants' medical notes on further antibiotics and other medications prescribed during the 28-day period after study entry.

## 6.6. Post-trial Treatment

Participants will only be asked to take their trial medication for seven days. After participants have finished taking their trial medication, they will receive usual clinical care.

## 7. SAFETY REPORTING

All adverse events, for patients randomised into the trial, should be reported from the time the parent or guardian signs the informed consent form until four weeks after randomisation. Depending on the nature of the event the reporting procedures below should be followed.

Any questions concerning adverse event reporting should be directed to the Study coordination centre in the first instance. A flowchart will be provided to aid in the reporting procedures.

Adverse events presenting to the participants GP or Hospital will be notified by the practitioner. In addition participants will carry a study card which highlights the need to notify their own doctor regarding adverse events. As a final check all participants will be asked to consent to a medical notes review which will take place after study recruitment at a time when any letters will have been returned from out-patient appointments. This enables us to be confident of detecting adverse events which have not been notified using the first two mechanisms.

Hospitalisations for elective treatment of a pre-existing condition do not need reporting as Serious Adverse Events (SAEs).

Adverse Event (AE)	Any untoward medical occurrence in a participant to whom a medicinal product has been administered, including occurrences
---------------------------	---

	which are not necessarily caused by or related to that product. These will not be collected for this study.
Adverse Reaction (AR)	An untoward and unintended response in a participant to an investigational medicinal product which is related to any dose administered to that participant. The phrase "response to an investigational medicinal product" means that a causal relationship between a trial medication and an AE is at least a reasonable possibility, i.e. the relationship cannot be ruled out. All cases judged by either the reporting medically qualified professional or the Sponsor as having a reasonable suspected causal relationship to the trial medication qualify as adverse reactions.
Serious Adverse Event (SAE)	A serious adverse event is any untoward medical occurrence that: 

• results in death

• is life-threatening

• requires inpatient hospitalisation (i.e an overnight stay) or prolongation of existing hospitalisation

• results in persistent or significant disability/incapacity

• consists of a congenital anomaly or birth defect.

 Other 'important medical events' may also be considered serious if they jeopardise the participant or require an intervention to prevent one of the above consequences. NOTE: The term "life-threatening" in the definition of "serious" refers to an event in which the participant was at risk of death at the time of the event; it does not refer to an event which hypothetically might have caused death if it were more severe.
Serious Adverse Reaction (SAR)	An adverse event that is both serious and, in the opinion of the reporting Investigator, believed with reasonable probability to be due to one of the trial treatments, based on the information provided.
Suspected Unexpected Serious Adverse Reaction (SUSAR)	A serious adverse reaction, the nature and severity of which is not consistent with the information about the medicinal product in question set out: 

• in the case of a product with a marketing authorisation, in the summary of product characteristics (SmPC) for that product in the case of any other investigational medicinal product, in the investigator's brochure (IB) relating to the trial in question.

Amoxicillin is a licensed medicine whose most common side-effects are mucocutaneous candidosis (thrush), diarrhoea, nausea, vomiting and rash (occurrence  $\geq 1/100$  to  $<1/10$ ). If these occur and are non-serious and of mild to moderate severity (based on clinician's assessment) an Adverse Event Report form will not be necessary. We will collect data on events such as severe reactions to the antibiotics such as anaphylaxis, severe allergy requiring steroid administration, emergency hospitalization for chest problems and severe Clostridium (antibiotic related diarrhoea).

Unexpected adverse reactions to beta-lactam antibiotics will be highly unlikely amongst trial participants, as the vast majority of children will have previously received beta-lactams to treat other infections. For non-serious adverse reactions to trial medication, the Chief Investigator or a designated alternative study clinician will assess the urgency with which the participant's treatment allocation should be unblinded.

## 7.1. Definitions

NB: to avoid confusion or misunderstanding of the difference between the terms "serious" and "severe", the following note of clarification is provided: "Severe" is often used to describe intensity of a specific event, which may be of relatively minor medical significance. "Seriousness" is the regulatory definition supplied above.

## 7.2. Causality

The relationship of each adverse event to the trial medication must be determined by a medically qualified individual according to the following definitions:

**Related:** The adverse event follows a reasonable temporal sequence from trial medication administration. It cannot reasonably be attributed to any other cause.

**Not Related:** The adverse event is probably produced by the participant's clinical state or by other modes of therapy administered to the participant.

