## 7.3. Procedures for Recording Adverse Events

The side effects of interest will be collected through the completion of the daily diary only.

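### Section 7 sets three causality thresholds and the strictest decides which SAEs reach expectedness review; its rules on collecting adverse events also conflict

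*Protocol*

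**What the plan says.** **Causality.** The definitions table in Protocol section 7 explains an adverse reaction as one where "a causal relationship between a trial medication and an AE is at least a reasonable possibility, i.e. the relationship cannot be ruled out". It accepts that judgement from either the reporting professional or the Sponsor. The serious adverse reaction row sets a different level: reasonable probability, in the reporting Investigator's opinion. Section 7.2 then gives the definitions to be used in practice: "The relationship of each adverse event to the trial medication must be determined by a medically qualified individual". Related requires plausible timing and a second condition: "It cannot reasonably be attributed to any other cause". Not Related applies when the child's clinical state or another therapy is the probable cause. Under section 7.4, the Chief Investigator or a delegate assesses expectedness for SAEs that have been reported as related, and section 7.6 covers SUSAR reporting.

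**Collection of adverse events.** Section 7 opens with "All adverse events, for patients randomised into the trial, should be reported", from consent to four weeks after randomisation. The adverse event row of the table that follows says "These will not be collected for this study". After the table, for listed common side effects that are non-serious and mild to moderate, "an Adverse Event Report form will not be necessary". Section 7.3 consists of one sentence: "The side effects of interest will be collected through the completion of the daily diary only".

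**The concern.** A safety section needs one causality rule, because the classification decides what happens next. Here the threshold in the definition of a reaction is lower than the one the assessor is told to use, and the assessor's answer decides whether expectedness is considered at all. All trial participants enter with an acute infection, so an event with two candidate causes is foreseeable. At stake is whether such an event, when serious, is examined as a possible SUSAR and so falls under the 7- and 15-day reporting limits of section 7.6.

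The collection rules raise a more practical problem. A site that reads the opening of section 7 will report every adverse event; a site that reads the table will report none that is non-serious. Uneven practice between sites would make the non-serious safety data hard to interpret. Section 5.19 adds to this: for withdrawn participants it refers to section 7.3 for monitoring adverse events, but that section offers only the diary.

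**Working it through.** No arithmetic applies, and the plan states no figure to reproduce. The check sets the definitions side by side and follows an SAE through them.

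**Thresholds**

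| Place in Protocol | Category | Test |
|---|---|---|
| Section 7, table | Adverse reaction | Link is a reasonable possibility and is not ruled out |
| Section 7, table | Serious adverse reaction | Link is reasonably probable |
| Section 7.2 | Related | Plausible timing and no other reasonable cause |
| Section 7.2 | Not Related | Another cause is probable |
| Section 7.4 | Goes to expectedness review | Reported as related |

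**Four cases, each an SAE with plausible timing**

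1. *Drug possible, no other reasonable cause.* Adverse reaction: yes. Section 7.2: Related. Expectedness is assessed. The definitions agree.
2. *Drug possible, another cause reasonable but not probable.* Adverse reaction: yes. Section 7.2: not Related, because another cause is reasonable, and not Not Related, because that cause is not probable. The event has no category and is not reported as related.
3. *Drug not ruled out, another cause probable.* Adverse reaction: yes. Section 7.2: Not Related. Expectedness is not assessed.
4. *Drug ruled out, another cause probable.* Adverse reaction: no. Section 7.2: Not Related. The definitions agree.

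The definitions disagree in cases 2 and 3, and in both the event stops before section 7.4's expectedness step. Case 2 also shows that the two categories in 7.2 are not complements. The serious adverse reaction row does not settle the matter: its test lies between the other two, so case 2 may or may not meet it, depending on how the reporting Investigator reads reasonable probability.

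**Collection rules**

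- Section 7, opening: all adverse events reported, to four weeks.
- Section 7, adverse event row: not collected.
- Section 7, after the table: no form for named mild or moderate effects, which implies a form for others.
- Section 7.2: a causality judgement for each adverse event, which presupposes that each is recorded.
- Section 7.3: side effects of interest from the diary only.

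The first and fourth cannot be carried out if the second is followed.

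**Diary length (minor).** Section 5.11 has the diary kept for at least one week and then while symptoms last, up to four weeks. Section 6.5 asks parents to record additional medicines in it from day 1 to day 28. The two give different diary periods.

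**The case against.** The strongest reply on causality is that nothing serious is lost. Section 7.4 sends every SAE to the coordinating centre within 24 hours whatever its cause, and sections 7.7 and 7.9 have the DSMC review SAEs after each recruitment season. The adverse-reaction definition also lets the Sponsor judge causality. Amoxicillin is licensed, and section 7 regards unexpected reactions as highly unlikely. The first two points stand: a reader might infer that possibly related SAEs go unreported, and the documents do not support that. What can be missed is the expectedness and SUSAR step. The Sponsor route helps less, because sections 7.4 to 7.6 describe no Sponsor causality review before expectedness. The Appendix E flowchart is not legible in the text available, so a further step there cannot be excluded; it would still have to agree with section 7.2.

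A reader might also infer that almost every SAE in these children has another explanation and would be called unrelated. The protocol gives no basis for that. The severe events it names include anaphylaxis and severe allergy, which are not obviously explained by a chest infection.

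On collection, the opening sentence of section 7 is followed by one that makes the procedure depend on the type of event, so it can be read as an umbrella over tiers: diary, named severe events, SAEs. That is probably the intent. It does not remove the conflict with the adverse event row, or with the requirement in 7.2 to judge each adverse event.

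Finally, a reader might infer that the side-effect comparison is biased because diary length follows recovery. The documents do not establish this. The minimum diary of one week covers the seven-day treatment course in both arms, section 6.5 points to 28 days of entries, and the comparison window can properly be left to the SAP.

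**Conclusion.** The point holds as an inconsistency in the current text. Section 7 contains three causality thresholds, and an assessor who follows section 7.2 exactly can keep a possibly related SAE out of expectedness and SUSAR assessment. The affected class is cases 2 and 3 above: SAEs where the drug cannot be ruled out but another cause is reasonable or probable. The protocol gives no expected SAE count or causality split, so the number cannot be estimated. It is likely to be small, since a SUSAR must also be inconsistent with the product information.

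The conclusion assumes that section 7.2 is applied as written and that no step outside the visible text reclassifies such events. The conflict over collecting adverse events needs neither assumption. No efficacy estimate is affected. Both faults should be corrected because the wording governs safety reporting and is cheap to align. The diary-period mismatch is a minor point of consistency.

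**What to change.** 1. Reconcile the definitions table in section 7 with sections 7.2 and 7.4 so that one causality threshold applies throughout. The protocol's own adverse-reaction definition supplies it: Related when a causal link is at least a reasonable possibility. Define Not Related as the complement, so that every SAE falls in exactly one category. Align the serious adverse reaction row, the SAE form and the Appendix E flowchart.
2. Replace the conflicting sentences in section 7 (opening, adverse event row and side-effect paragraph), 7.2 and 7.3 with one statement of which events are collected, by which route (diary, practitioner report or notes review) and over what period. Limit the causality requirement in 7.2 to the events actually collected, and check the cross-reference from section 5.19.
3. Make the diary period for side effects consistent between sections 5.11 and 6.5.

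The cost is a wording amendment to the protocol and SAE form, and possibly a few more SAEs sent for expectedness review. Treatment, visits and sample size are unchanged.
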